4 STUDY VARIABLES

See Section 13.1 for the definition of analysis sets.

4.1 Primary variables

4.1.1 Pharmacokinetic and immunological variables

Certolizumab pegol plasma concentrations and anti-CZP antibody levels at Week 16 and Week 48 will be assessed and data will be summarized.

4.1.2 Safety variables

The primary safety variables will be the incidence of serious TEAEs and TEAEs leading to permanent withdrawal of IMP.

Adverse events will be solicited at every visit, recorded and coded according to Medical Dictionary for Regulatory Activities (MedDRA[®]) criteria.

4.2 Secondary variables

Efficacy will be assessed by the PedACR30, PedACR50, PedACR70, and PedACR90 response rates at Week 16 as compared to Baseline (see Section 11.1 for definition).

4.3 Other variables

Other PK and immunological variables are:

- Certolizumab pegol plasma concentrations and anti-CZP antibody levels at other study timepoints

Other safety variables are:

- Incidence of TEAEs, TEAEs of interest, TEAEs by relatedness, TEAEs by severity, and TEAEs by duration of exposure
- Clinical laboratory values (hematology, biochemistry, and urinalysis) will be collected and assessed at every visit except Visits 3 and 4 and Unscheduled Visits.
- Vital sign abnormalities will be evaluated at every visit.
- Assessments of study participant's developmental stages and growth (height, weight) will be performed to determine Tanner stages at Baseline, every 24 weeks thereafter, and the Early Discontinuation/End of Treatment Visit (weight at every visit through Final Visit). For study participants enrolled prior to Protocol Amendment 9, Tanner stages assessment will be performed every 48 weeks following Protocol Amendment 8, and only for those subjects who have not reached Tanner stage V.
- Autoantibody (antinuclear antibodies [ANA] and anti-double-stranded deoxyribonucleic acid [anti-dsDNA] antibodies) concentrations will be evaluated at Baseline (testing for anti-dsDNA antibodies only if ANA is positive), Weeks 16 and 48, and at the Early Discontinuation/End of Treatment Visit.

Other efficacy and health outcomes variables are:

- PedACR30, PedACR50, PedACR70, and PedACR90 response rates at every visit except Week 16 and Final Visit as compared to Baseline (see Section 11.1 for definition).
- Change from Baseline in number of joints with active arthritis at every visit except Final Visit.
- Change from Baseline in number of joints with limitation of range of motion at every visit except Final Visit.
- Change from Baseline in Physician's Global Assessment of Disease Activity (VAS) at every visit except Final Visit.
- Change from Baseline in CHAQ at every visit except Final Visit.
- Change from Baseline in Parent's Assessment of Arthritis Pain (VAS) at every visit except Final Visit.
- Change from Baseline in Parent's Global Assessment of Overall Well-Being (VAS) at every visit except Final Visit.
- Ratio to Baseline in CRP at every visit except Final Visit.
- Change from Baseline in JADAS at every visit except Final Visit.
- Percentage of study participants with Clinically Inactive Disease (CID), as defined in Section 11.10, at every post-Baseline visit except Final Visit.
- Percentage of study participants with clinical remission on medication (CRM), as defined in Section 11.10, at every post-Baseline visit from Week 24 onwards except Final Visit.
- Time (in days) to CID.
- Time (in days) to CRM.
- Change from Baseline in DMS at every visit except Final Visit.
- Change from Baseline in FPS-R (child-reported, ages 5 to 11 years), daily during the first week of treatment; Weeks 4, 12, 16, 24, and then every 8 weeks thereafter through the Early Discontinuation/End of Treatment Visit. For study participants enrolled prior to Protocol Amendment 9, visit frequency changes to every 16 weeks instead of every 8 weeks following implementation of Protocol Amendment 8.
- Change from Baseline in JIA Pain VAS, daily during the first 7 days of the study (acute and standard versions); and at Weeks 4, 12, 16, 24, and then every 8 weeks thereafter through the Early Discontinuation/End of Treatment Visit (standard version) for study participants ages 12 to 17 years. For study participants enrolled prior to Protocol Amendment 9, visit frequency changes to every 16 weeks instead of every 8 weeks following implementation of Protocol Amendment 8.
- Change from Baseline in Fatigue Assessment Scale at every visit except Weeks 12 and 20, and Final Visit.

- Juvenile Arthritis School Attendance and Caregiver Work Productivity Survey responses at Baseline, Week 4, and every visit thereafter except Final Visit.

5 STUDY DESIGN

5.1 Study description

This is a Phase 3, multicenter, open-label study to assess the PK, safety, and efficacy of CZP in children and adolescents with moderately to severely active polyarticular-course JIA.

Please refer to Study Schedule of Assessments in Section 5.2 for visit-specific procedures and to Section 5.3 for a schematic representation of the study.

The overall study consists of a Screening Period of up to 4 weeks (between Weeks -4 to 0 [Visits 1 and 2]) and an open-label Treatment Period which will continue until the approval of the marketing application for the polyarticular-course JIA indication in the study participant's country or region or until further notice from UCB. A Final Visit will be conducted 12 weeks after last dose of study medication.

A Screening Visit is used to initiate assessments of eligibility. Certolizumab pegol will be administered as a fixed dose based on weight throughout the study (see Table 7-1 for doses administered and Section 5.4.2 for the rationale for the different dose regimens). At Baseline (Week 0, Visit 2) eligible study participants will begin with 3 loading doses of CZP at Weeks 0, 2, and 4 followed by a maintenance dose for the duration of the study. After Week 4 (Visit 5), home-based CZP administration by the study participant or parent/caregiver will be permitted between scheduled study visits.

Interim analyses were performed as described in Section 13.7. A full interim analysis will be performed after all active study participants have completed the Week 24 (Visit 10) assessments.

Pharmacokinetic data from this study that were assayed with an enzyme-linked immunosorbent assay (ELISA) technique will not be used for submission to the Food and Drug Administration (FDA) to complete the Pediatric Research Equity Act commitment, primarily due to deficiencies detected with the use of the bioanalytical assay within RA0043. All study participants enrolled following Protocol Amendment 9 will have plasma concentrations of CZP and anti-CZP antibodies analyzed using an ECLIA method that meets current regulatory standards. In addition, PK and ADA samples (for which sufficient volume is available) collected in this study prior to Protocol Amendment 9 will be analyzed with the ECLIA method. The collective ECLIA-based PK data for this study will form the basis of any future CZP modeling and simulation work.

5.1.1 Study duration per study participant

For each study participant, there will be a Screening Period of up to 4 weeks (Weeks -4 to 0). Eligible study participants will subsequently initiate open-label treatment with CZP at Baseline (Week 0, Visit 2) and be permitted to continue until the approval of the marketing application for the polyarticular-course JIA indication in the study participant's country or region, or until further notice from UCB. The Final Visit will be conducted 12 weeks after the last dose of study medication.

The end of the study is defined as the date of the last study participant's Final Visit.

First Study participant, First Visit – 1Q 2012

Planned Last Study participant, First Visit – 3Q 2021

5.1.2 Planned number of study participants and sites

Approximately 195 study participants are planned to be screened at about 55 centers in order to enroll 156 study participants in this study, as follows:

- A minimum of 10 study participants will be enrolled on the reduced CZP dose regimen in each weight range of 10 to <20kg (22 to <44lb), 20 to <40kg (44 to <88lb), and \geq 40kg (\geq 88lb) (See Section 7.2 for the doses administered in the study and Section 5.4.2.2 for the rationale for the reduced CZP dose regimen).
- A minimum of 10 study participants will be enrolled in each age category of 2 to 5 years, 6 to 11 years, and 12 to 17 years, irrespective of the dose regimen.
- A minimum of 25 study participants will be enrolled who receive CZP as monotherapy (ie, study participants with established intolerance or inadequate response to MTX), irrespective of the dose regimen.
- A minimum of 10 study participants with ERA will be enrolled, irrespective of the dose regimen.
- The enrollment per site is limited to a maximum of 15 study participants.

Recruitment based on all protocol amendments prior to Protocol Amendment 9 is complete. Following Protocol Amendment 9, an additional 30 study participants will be enrolled on the original dose regimen with the aim to enroll at least 5 study participants in each weight range of 10 to <20kg (22 to <44lb), 20 to <40kg (44 to <88lb), and \geq 40kg (\geq 88lb) (See Section 7.2 for the doses administered in the study and Section 5.4.2.1 for the rationale for the original CZP dose regimen).

Each of these categories is assessed independently. For instance, a 12kg, 3-year old study participant unable to tolerate MTX contributes to the enrollment goals for the 10 to <20kg (22 to <44lb) weight group, the 2- to 5-year-old age group, and the CZP as monotherapy group.

5.1.3 Anticipated regions and countries

The regions planned for participation in this study are North and South America and Russia, with possible extension to other regions.

5.2 Schedule of study assessments

Table 5-1 Schedule of study assessments

| Study period | Screening | Baseline | | | | | | | |
|---|------------------------|------------------|---|---|---|--|--------------------------------|------------------------------------|-------------------------------|
| Week | -4 to 0 ^(a) | 0 | 1 | 2 | 4, 8, 12, 16, (17 ^(u)), 20, 24 | 32 and every 8 weeks thereafter ^(z) | Unsch. Visit ^(b) | Early Disc/ End of Treatment | Final Visit ^(c) |
| Visit (+/-3 days) ^(a) | 1 | 2 | 3 | 4 | 5 to 10 | 11 onwards | | | FV |
| Written informed consent/assent | X | | | | | | | | |
| Assessment of inclusion/exclusion criteria | X | X | | | | | | | |
| Demography, JIA history, prior JIA medication, general medical and procedure history | X | | | | | | | | |
| Vital signs ^(d) | X | X | X | X | X | X | X | X | X |
| Height | X ^(e) | X | | | X ^(f) | X ^(f) | | X ^(f) | |
| Weight ^(g) | X ^(e) | X | X | X | X | X | | X | X |
| Tanner stages (except growth) | | X | | | X ^(f) | X ^(f) | | X ^(f) | |
| Physical examination ^(h) | X | X | | | X | X | | X | X |
| TB questionnaire | X | X | | | X ⁽ⁱ⁾ | X ⁽ⁱ⁾ | | X ⁽ⁱ⁾ | |
| Hematology/biochemistry/urinalysis ^(j) | X ^(k) | X ^(l) | | | X | X | | X | X |
| Reproductive potential and birth control | X | X | | | X | X | | X | X |
| Pregnancy testing ^(m) | X | X | | | X ^(m) | X | | X | X |
| C-reactive protein ⁽ⁱ⁾ | X | X | X | X | X | X | | X | |
| TB screening ⁽ⁿ⁾ and chest x-ray ^(o) | X | | | | | X ⁽ⁿ⁾ | | | |
| PRINTO/PRCSG standard joint examination | X | X | X | X | X | X | | X | |
| Physician's Global Assessment of Disease Activity | X | X | X | X | X | X | | X | |
| CHAQ-parent reported | X | X | X | X | X | X | | X | |
| Parent's Assessment of Arthritis Pain | X | X | X | X | X | X | | X | |
| Parent's Global Assessment of Overall Well-Being | X | X | X | X | X | X | | X | |
| Clinically Inactive Disease and clinical remission ^(p) | | | X | X | X | X | | X | |
| Duration of morning stiffness | | X | X | X | X | X | | X | |
| JADAS | | X | X | X | X | X | | X | |

Table 5-1 Schedule of study assessments

| Study period | Screening | Baseline | | | | | | | |
|---|------------------------|------------------|---|---|---|--|--------------------------------|------------------------------------|-------------------------------|
| Week | -4 to 0 ^(a) | 0 | 1 | 2 | 4, 8, 12, 16, (17 ^(u)), 20, 24 | 32 and every 8 weeks thereafter ^(z) | Unsch. Visit ^(b) | Early Disc/ End of Treatment | Final Visit ^(c) |
| Visit (+/-3 days) ^(a) | 1 | 2 | 3 | 4 | 5 to 10 | 11 onwards | | | FV |
| Faces Pain Scale-Revised ^(q) | | X | | | X | X | | X | |
| Patient's Assessment of Arthritis Pain ^(r) , acute | | X | | | | | | | |
| Patient's Assessment of Arthritis Pain ^(r) , standard | | X | | | X ^(r) | X | | X | |
| Fatigue Assessment Scale | | X | X | X | X ^(s) | X | | X | |
| Juvenile Arthritis School Attendance and Caregiver Work Productivity Survey (parent/caregiver-reported) | | X | | | X | X | | X | |
| Concomitant medications and procedures ^(t) | X | X | X | X | X | X | X | X | X |
| Adverse events | X | X | X | X | X | X | X | X | X |
| IXRS contact | X | X | X | X | X | X | | X | X |
| CZP plasma concentrations | | X | X | | X ^(u) | X ^(v) | | | |
| Anti-CZP antibodies | | X | X | | X ^(u) | X ^(v) | | | |
| Autoantibodies (ANA and anti-dsDNA antibodies) ^(l) | | X ^(w) | | | X ^(x) | X ^(x) | | X | |
| CZP administration ^(y) | | X | | X | X | X | | | |

ANA=antinuclear antibody; anti-dsDNA=anti-double-stranded deoxyribonucleic acid; BCG=Bacille Calmette-Guérin; CHAQ=Childhood Health Assessment Questionnaire; CZP=certolizumab pegol; Disc=discontinuation; IGRA=interferon-gamma release assay; IXRS=interactive voice/web response system; JADAS=Juvenile Arthritis Disease Activity Score; JIA=juvenile idiopathic arthritis; PRINTO/PRCSG=Paediatric Rheumatology International Trials Organisation/Pediatric Rheumatology Collaborative Study Group; TB=tuberculosis; TST=tuberculin skin test; Unsch=Unscheduled

- ^a Screening Visit must be completed at least 4 to 12 working days prior to the Baseline Visit, depending on regional requirements and laboratory assessments required for the study participant (please refer to Section 10.6 and the laboratory manual). For all other visits, the Visit window is ±3 days relative to Baseline.
- ^b Vital signs, concomitant medications, concomitant procedures, and AEs must be assessed at every Unscheduled Visit. Other PK and safety assessments should be performed as related to nature of the visit. For Unscheduled Visits related to the dose changes, see Sections 7.2.1 and 8.6.1. For these Unscheduled Visits, the same visit window applies, ie, ±3 days.
- ^c Final Visit should be performed 12 weeks after the final dose of CZP.
- ^d Pulse, systolic/diastolic blood pressure, and temperature to be measured within approximately 15 minutes prior to dosing and in addition (pulse and blood

Table 5-1 Schedule of study assessments

| Study period | Screening | Baseline | | | | | | | |
|----------------------------------|------------------------|----------|---|---|---|--|--------------------------------|------------------------------------|-------------------------------|
| Week | -4 to 0 ^(a) | 0 | 1 | 2 | 4, 8, 12, 16, (17 ^(u)), 20, 24 | 32 and every 8 weeks thereafter ^(z) | Unsch. Visit ^(b) | Early Disc/ End of Treatment | Final Visit ^(c) |
| Visit (+/-3 days) ^(a) | 1 | 2 | 3 | 4 | 5 to 10 | 11 onwards | | | FV |

pressure only) approximately 30 minutes after dosing.

- ^e Change in height and weight over the last 6 months and over the last year will be collected via parent-/self-report, if not available from medical records.
- ^f Height and Tanner stages to be measured at Week 24 and 48, every 24 weeks thereafter (for study participants enrolled prior to Protocol Amendment 9, Tanner stages assessment will be performed every 48 weeks following Protocol Amendment 8, and only for those subjects who have not reached Tanner stage V) and at Early Discontinuation/End of Treatment.
- ^g From Week 2 onwards, weight measurements will be used to readjust the CZP dose as needed according to [Table 7-1](#).
- ^h Physical examination findings (except joint examination) are recorded in the CRF only at Screening. Subsequent physical examinations are to be recorded in the source documentation and clinically significant findings recorded as AEs.
- ⁱ TB questionnaire to be completed at Weeks 12 and 24 and every 16 weeks thereafter, and Early Discontinuation/End of Treatment. If the Investigator suspects latent TB or active TB, TB testing and/or a chest x-ray should be performed as outlined in [Section 10.7.9](#).
- ^j Hematology/biochemistry/urinalysis will be performed by a central laboratory, except urine dipsticks, which will be done locally at the site. Study participants do not have to be fasting.
- ^k At Screening, laboratory testing includes testing for hepatitis B core antibody, hepatitis B surface antibody, hepatitis B surface antigen, hepatitis C virus antibody, and HIV 1/2. Study participants with a positive hepatitis B virus test will not be allowed in the study (except for anti-hepatitis B surface positive only, in case study participant is immune due to well-documented hepatitis B vaccination or isolated false-positive anti-hepatitis B core test confirmed with a confirmatory test such as hepatitis B virus deoxyribonucleic acid [DNA]). A positive hepatitis C antibody test will be confirmed by a confirmatory test (such as hepatitis C virus ribonucleic acid [RNA]) and those with a positive confirmatory test will not be allowed in the study.
- ^l At Baseline, hematology/chemistry/urinalysis only need to be done if in the Investigator's opinion there is a change in the study participant's status compared to the Screening Visit.
- ^m Pregnancy testing for postmenarcheal female study participants. Serum testing by a central laboratory at Screening and urine testing locally at the site at Baseline, Weeks 8, 16, 24, and every visit thereafter.
- ⁿ TB screening: Interferon-gamma release assay (IGRA) testing (QuantiFERON[®]) is required to be performed by the central lab for all study participants from 5 to 17 years of age. TST and IGRA testing at Screening is mandatory for study participants less than 5 years of age in this study unless written documentation of BCG vaccination is available (refer to [Section 6.2](#) [exclusion criterion 11] and [Section 10.7.9](#)). Following implementation of Protocol Amendment 7, IGRA testing (QuantiFERON) should be done once a year (approximately every 48 weeks) for all study participants.
- ^o Chest radiographic imaging is done at Screening and results must be available at Baseline before first drug administration, unless a chest x-ray or CT is available within 2 months prior to Screening.
- ^p Clinical remission on medication will be assessed at every post-Baseline visit from Week 24 onwards only.

Table 5-1 Schedule of study assessments

| Study period | Screening | Baseline | | | | | | | |
|----------------------------------|------------------------|----------|---|---|---|--|--------------------------------|------------------------------------|-------------------------------|
| Week | -4 to 0 ^(a) | 0 | 1 | 2 | 4, 8, 12, 16, (17 ^(u)), 20, 24 | 32 and every 8 weeks thereafter ^(z) | Unsch. Visit ^(b) | Early Disc/ End of Treatment | Final Visit ^(c) |
| Visit (+/-3 days) ^(a) | 1 | 2 | 3 | 4 | 5 to 10 | 11 onwards | | | FV |

^q For study participants ages 5 to 11 years. Daily assessment during the first week (Baseline and Day 1 to Day 7, to be collected at Week 1). In addition, to be completed at Weeks 4, 12, 16, 24, and then every 8 weeks thereafter (for study participants enrolled prior to Protocol Amendment 9, visit frequency changes to every 16 weeks instead of every 8 weeks following implementation of Protocol Amendment 8) through the End of Treatment/Early Discontinuation Visit.

^r For study participants ages 12 to 17 years. Daily assessment of acute VAS version during the first week (at Baseline and Day 1 to Day 7, to be collected at Week 1). In addition, standard VAS version to be completed at Baseline, Weeks 4, 12, 16, 24, and then every 8 weeks thereafter (for study participants enrolled prior to Protocol Amendment 9, visit frequency changes to every 16 weeks instead of every 8 weeks following implementation of Protocol Amendment 8) through the End of Treatment/Early Discontinuation Visit for study participants ages 12 to 17 years.

^s Fatigue Assessment Scale performed at Weeks 4, 8, 16, and 24.

^t Concomitant procedures are collected starting at Baseline.

^u CZP plasma concentration and anti-CZP antibodies to be measured at Weeks 4, 12, 16, and 24. A postdose CZP plasma sample will be collected at approximately 5 to 7 days following the Week 16 Visit (ie, requires an additional clinic site visit for blood collection at Week 17). Samples for CZP plasma concentration and anti-CZP antibodies will be collected as separate samples.

^v CZP plasma concentration and anti-CZP antibodies to be measured at Weeks 32, 40, 48, and every 24 weeks thereafter for study participants enrolled following Protocol Amendment 9. For study participants enrolled prior to Protocol Amendment 9, samples for CZP plasma concentration and anti-CZP antibodies will no longer be collected. Samples for CZP plasma concentration and anti-CZP antibodies will be collected as separate samples.

[figure not shown]
^w At Baseline, testing for anti-dsDNA antibodies will only be done if ANA is positive.

^x ANA and anti-dsDNA antibodies performed at Week 16 and Week 48.

^y After Week 4 (Visit 5) study participants/caregivers may administer CZP Q2W (or Q4W for the lowest weight group) at home between scheduled study visits. See Section 7.2 regarding training and option for continued site administration.

^z For study participants enrolled prior to Protocol Amendment 9, on-site CZP administration, safety sampling, and efficacy assessment frequency changes to every 16 weeks instead of every 8 weeks following implementation of Protocol Amendment 8, provided that compliance is maintained with the CZP dosing schedule using at-home administration. The option to come to the site for CZP administration between scheduled visits is available as needed.

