The original choice of dose and the weight-based dose-adjustment algorithm was supported by simulations of the PK exposure and response rates in children using the PopPK model and PK/PD exposure response model developed in adult RA study participants, corrected for pediatric demographics (C87079 addendum 08 Oct 2008). Results of these simulations showed that all age groups exhibit similar exposures (C_{max} and AUC_T) to those of adults over the Week 14 to Week 16 dosing interval, with the pediatric/adult ratio of the median predicted values of PK parameters ranging from 1.03 to 1.19 for C_{max} and from 0.97 to 1.18 for AUC_T. The similarities in exposures were reflected in the probability of ACR20 response, which are similar for all age groups at Week 16 (pediatric/adult ratio of the median predicted values ranging from 1.08 to 1.10). These simulations were performed upon the assumption that disease progression and response rate for a given exposure are similar in children and adults.

The original CZP dose regimen is the regimen that will be used for study participants enrolled following Protocol Amendment 9.

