7.2 Treatments to be administered

Throughout the study, CZP dosing is fixed dose based on weight and given Q2W, with the exception of the lowest weight group on the reduced CZP regimen who will receive the maintenance dose Q4W. The loading dose, maintenance dose, and range of exposures in each weight category for both the original and reduced CZP regimens are presented in [Table 7-1](#). Study participants start with 3 loading doses of CZP at Weeks 0, 2, and 4 followed by a maintenance dose for the duration of the study. After Week 4 (Visit 5), home-based CZP administration by the study participant or parent/caregiver will be permitted between scheduled study visits.

A study participant's dosing category will only be changed after the confirmation of a weight change by the Investigator **at a scheduled clinic visit**.

The study participant will receive the dose of the next weight category once their weight crosses the 40kg/88lb boundary or crosses the 20kg/44lb boundary at a scheduled clinic visit. The study participant will continue on the dose of the new weight category regardless of potential decrease of the weight below the boundary. In case of significant weight fluctuations the Investigator should contact the Medical Monitor to discuss and confirm potential change in dosing if medically advised or discontinuation of treatment (eg, if related to AE).

The injection should be administered at either the lateral abdominal wall or upper outer thigh. Treatment of the injection site with an anesthetic cream prior to dosing is permitted.

Table 7-1 Dosing administration of CZP^a

| Weight range | Loading dose – Weeks 0, 2, and 4 (mg/kg dose range) IMP Description | Maintenance – Week 6 and onwards (mg/kg dose range) IMP Description |
|------------------------------|---|---|
| Original CZP regimen | | |
| 10 to <20kg (22 to <44lb) | 100mg Q2W (5-10mg/kg) 1 x 0.5mL inj | 50mg Q2W (2.5-5mg/kg) 1 x 0.25 mL inj |
| 20 to <40kg (44 to <88lb) | 200mg Q2W (5-10mg/kg) 1 x 1mL inj | 100mg Q2W (2.5-5mg/kg) 1 x 0.5mL inj |
| ≥40kg (≥88lb) | 400mg Q2W (<10mg/kg) 2 x 1mL inj | 200mg Q2W (<5mg/kg) 1 x 1mL inj |
| Reduced CZP regimen | | |
| 10 to <20kg (22 to <44lb) | 50mg Q2W (2.5-5mg/kg) 1 x 0.25mL inj | 50mg Q4W (2.5-5mg/kg) 1 x 0.25mL inj |
| 20 to <40kg (44 to <88lb) | 100mg Q2W (2.5-5mg/kg) 1 x 0.5mL inj | 50mg Q2W (1.25-2.5mg/kg) 1 x 0.25mL inj |
| ≥40kg (≥88lb) | 200mg Q2W (<5mg/kg) 1 x 1mL inj | 100mg Q2W (<2.5mg/kg) 1 x 0.5mL inj |

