The method of injection (ie, qualified site personnel-injection at study site; injection by the study participant/caregiver or qualified health care professional at the study site or at home) and the site of injection (abdomen, thigh) will be recorded in the CRF at each visit.

Study participants achieving clinical remission on medication (CRM), ie, after 6 months of continuous CID, may discontinue CZP treatment at the Investigator's discretion following consultation with the Sponsor to confirm remission status. Study participants who have discontinued CZP due to achieving CRM will be allowed to remain in the study and continue with scheduled study visits. Study participants not maintaining persistent CID following achievement of CRM will be allowed to resume CZP treatment at any time at the Investigator's discretion and consultation with the Sponsor. If a study participant is on concomitant MTX treatment, the Investigator may decide to decrease and ultimately discontinue the MTX dose after complete discontinuation of CZP. Study participants not maintaining persistent CID following achievement of CRM and resuming treatment will restart the fixed-dose CZP dosing based on their current weight with 3 loading doses of CZP administered Q2W over 6 weeks, followed by a maintenance dose administered Q2W, or Q4W for the lowest weight group on the reduced CZP regimen for the duration of the study (see [Table 7-1](#)).

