7.2.1 Procedure for dose change (Protocol Amendment 9)

Following Protocol Amendment 9, study participants will only be enrolled on the original CZP dose regimen. With Protocol Amendment 4, the maintenance dose in the study was reduced by 50% for all weight groups (not applicable for study participants enrolled on the reduced CZP dose regimen per Protocol Amendment 5). Participants on the reduced CZP dose regimen can remain on the reduced CZP dose or may be switched to the original CZP dose regimen at the discretion of the Investigator and in consultation with the medical monitor. Additional dose changes are not allowed. The procedure for dose change is as follows:

- The timepoint of the dose change is the next scheduled time of injection after the Informed Consent form related to the dose change was signed. In case the next scheduled injection was planned for home dosing, the study participant will be requested to return to the clinic for an Unscheduled Visit for signing the Informed Consent form related to the dose change, administration of CZP, and to dispense the new supplies. Unused IMP dispensed previously needs to be returned.
In case the study participant is not able to visit the site for that next scheduled injection, then the dose change must be performed at the next scheduled injection.

- Study participants will be monitored at least every 4 weeks over a period of 12 weeks after the dose change, either at the regularly scheduled visits or at additional Unscheduled Visits. The Unscheduled Visits will be scheduled to match with the dosing schedule, ie, the study medication will be administered at the day of the Unscheduled Visit. The Investigator should consult with the Medical Monitor in case of any questions related to the timing of the dose change or the Unscheduled Visits.
 - Study participants undergoing the dose change at an Unscheduled Visit between the regular visits will be required to return at the latest after 4 weeks for an Unscheduled Visit in case no regular visit is scheduled within 4 weeks. These study participants will be monitored at least every 4 weeks over a period of 12 weeks.

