Study participants achieving CRM, ie, after 6 months of continuous CID, may discontinue CZP treatment at the Investigator’s discretion following consultation with the Sponsor to confirm remission status. Study participants who have discontinued CZP due to achieving CRM will be allowed to remain in the study and continue with scheduled study visits. Study participants not maintaining persistent CID following achievement of CRM will be allowed to resume CZP treatment at any time at the Investigator’s discretion and consultation with the Sponsor. If a study participant is on concomitant MTX treatment, the Investigator may decide to decrease and ultimately discontinue the MTX dose after complete discontinuation of CZP. Study participants not maintaining persistent CID following achievement of CRM and resuming treatment will restart the fixed-dose CZP dosing based on their current weight with 3 loading doses of CZP administered Q2W over 6 weeks, followed by a maintenance dose administered Q2W for the duration of the study, with exception of the lowest weight group on the reduced dose regimen, who will receive the maintenance dose Q4W.

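### Table 5-1 footnote y gives a Q4W home-dosing interval for the lowest weight group without naming a regimen, which contradicts Table 7-1 for 10 to <20kg participants on the original regimen

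*Protocol*

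**What the plan says.** **Schedule of assessments.** Footnote y to the CZP administration row of Table 5-1 (Section 5.2) says that after Week 4 participants or caregivers "may administer CZP Q2W (or Q4W for the lowest weight group) at home between scheduled study visits". It then refers to Section 7.2, but only for training and for the option of continued dosing at the site.

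**Dosing section.** Section 7.2 makes dosing Q2W throughout, "with the exception of the lowest weight group on the reduced CZP regimen who will receive the maintenance dose Q4W". Table 7-1 has two maintenance entries for 10 to <20kg:

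- Original regimen (loading, then maintenance): "100mg Q2W (5-10mg/kg) 1 x 0.5mL inj | 50mg Q2W (2.5-5mg/kg) 1 x 0.25 mL inj".
- Reduced regimen (maintenance): "50mg Q4W (2.5-5mg/kg) 1 x 0.25mL inj".

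**Restart after loss of inactive disease.** Section 7.2 allows Q2W "or Q4W for the lowest weight group on the reduced CZP regimen for the duration of the study". Section 11.10 repeats the rule, "with exception of the lowest weight group on the reduced dose regimen, who will receive the maintenance dose Q4W".

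**Who is on which regimen.** Section 5.4.2.1 states: "The original CZP dose regimen is the regimen that will be used for study participants enrolled following Protocol Amendment 9". Section 7.2.1 agrees: "Following Protocol Amendment 9, study participants will only be enrolled on the original CZP dose regimen". Sections 5.4.2.2 and 7.2.1 let earlier participants stay on the reduced regimen or be switched to the original one.

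**The concern.** Where the other passages state Q4W as a maintenance rule, they tie it to two conditions: the lowest weight group and the reduced regimen. Footnote y keeps the first and omits the second. For a 10 to <20kg child on the original regimen, the schedule table and the dosing table therefore give different intervals.

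Amendment 9 enrolls 30 further participants to obtain exposure and safety data on the original regimen with the validated ECLIA assay. It aims for at least 5 in each weight range, including 10 to <20kg (Section 5.1.2). CZP concentrations at Weeks 16 and 48 are primary variables (Section 4.1.1), and Section 5.4.1 builds the paediatric programme on matching exposure to adults. A dosing interval that can be read two ways in a stratum this small bears directly on those data.

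**Working it through.** The protocol gives no figure to reproduce. The check compares the passages and then counts doses.

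**1. Passages side by side, 10 to <20kg, maintenance**

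| Place | Original regimen | Reduced regimen |
|---|---|---|
| Table 5-1 footnote y | Q4W (no regimen named) | Q4W (no regimen named) |
| Section 7.2, opening paragraph | Q2W | Q4W |
| Table 7-1 | 50mg Q2W | 50mg Q4W |
| Section 7.2, restart | Q2W | Q4W |
| Section 11.10, restart | Q2W | Q4W |

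Only the footnote's original-regimen cell differs. Its pointer to Section 7.2 does not concern the interval, so it does not supply the missing condition. Footnotes q, r, v and z of the same table do distinguish participants enrolled before Amendment 9 from those enrolled after it. Footnote y does not.

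**2. Dosing weeks in Section 8.4.** The between-visit doses are at Weeks 6, 10, 14, 18, 22, 26, 28 and 30. With dosing at the visits (Weeks 8, 12, 16, 20, 24, 32) the sequence is 6, 8, 10, ..., 30, 32, which is every 2 weeks.

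**3. Doses under each reading, original-regimen child of 10 to <20kg, 50mg per dose**

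- Weeks 6 to 24, Q2W: (24 - 6)/2 + 1 = 10 doses, 10 x 50 = 500mg.
- Weeks 6 to 24, Q4W: Weeks 8, 12, 16, 20, 24 (or 6, 10, 14, 18, 22) = 5 doses, 5 x 50 = 250mg.
- From Week 32, per 8-week visit interval, Q2W: 1 at the visit and 3 at home (+2, +4, +6 weeks) = 4 doses, 200mg.
- From Week 32, per 8-week visit interval, Q4W: 1 at the visit and 1 at home (+4 weeks) = 2 doses, 100mg.

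The ratio is 250/500 = 100/200 = 0.5.

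**4. Concentration, conditional on the Q4W reading being followed.** If exposure is proportional to dose, the average concentration is also about half. The Introduction reports an approximately linear dose-exposure relation for single doses, so this is a reasonable assumption but still an assumption.

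The primary samples are taken predose (Sections 8.4 and 9), so the trough could fall further. Assume one compartment, fast absorption and steady state, and let r be the fraction remaining after 14 days. The Q2W trough is proportional to r/(1 - r) and the Q4W trough to r²/(1 - r²), so their ratio is r/(1 + r).

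- Half-life 14 days (Introduction): r = 0.5, ratio = 0.5/1.5 = 33%.
- CL/F 0.253 and V/F 2.90 (Table 13-1, ages 4 to 8; units taken as L/day and L): k = 0.253/2.90 = 0.0872 per day, half-life = 0.693/0.0872 = about 8 days, r = exp(-0.0872 x 14) = 0.295, ratio = 0.295/1.295 = 23%.

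These two ratios are illustrations. Slow subcutaneous absorption, or residue from the loading doses at Week 16, would move them.

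**5. How the child would be analysed.** Section 13.2.1 assigns the subgroup by the regimen on which treatment began, with 1 or more doses received. A new participant qualifies during loading, before the footnote has any effect, and so would be summarised as original regimen.

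**The case against.** The strongest reply is that this is incomplete wording in a permissive footnote and that the interval is fixed elsewhere. Section 5.1 sends the reader to Table 7-1 for doses. Footnote g of the same schedule table does the same for weight-based adjustment. The note under Table 7-1 says which participants follow the original regimen, and the weeks in Section 8.4 fit Q2W. There are also controls. IXRS allocates containers up to the next visit, families receive written dosing instructions and record each home dose, and accountability is checked at every visit. Missing 3 doses in 12 months prompts a decision on withdrawal (Section 7.7); measured against Table 7-1, a child on the Q4W reading would reach that count at Week 14 (Weeks 6, 10 and 14).

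This stands as an argument about likelihood. It does not remove the contradiction, and the IXRS settings are not in the document, so it cannot be shown that they follow Table 7-1 and not the footnote.

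Three stronger readings are tempting and are not supported:

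- *That the footnote conflicts with dosing for everyone under Amendment 9.* It concerns only the lowest weight group. Within that group it agrees with Table 7-1 for children who remain on the reduced regimen, which the amendment allows.
- *That new participants will in fact receive half the doses in Table 7-1.* This requires a site to follow the footnote over Table 7-1 and the controls not to catch it. Nothing in the document gives a probability for that.
- *That sites dispense from the schedule table.* The protocol does not say so. It describes IXRS allocation.

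The analysis consequence also has limits. Section 13.1 excludes important deviations affecting PK from the PK-PP population, so a child recognised as a deviation could be dropped and not misclassified, which would thin the stratum instead. Participants enrolled before Amendment 9 no longer give PK samples. A switch to the original regimen therefore affects their safety exposure periods (Section 13.3) but not the primary concentrations.

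**Conclusion.** The inconsistency is real and confined to 10 to <20kg participants on the original regimen: those enrolled following Amendment 9, and earlier participants switched to that regimen. It is a wording conflict, not a flaw in the design.

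If the footnote were followed for such a child, maintenance doses would be half those in Table 7-1, and the average concentration would be about half if exposure is dose-proportional. The primary PK effect applies to new enrollees, of whom at least 5 of 30 are aimed for in this band, so even one or two affected children would matter to that stratum's Week 16 and Week 48 summaries. The number of switched participants still under 20kg is not given. No view is taken here on which interval is clinically right.

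**What to change.** Reconcile Table 5-1 footnote y with Section 7.2, Table 7-1 and Section 11.10, so that the protocol states one interval for each combination of regimen and weight group. Then check that IXRS home-dispensing quantities for 10 to <20kg participants, both newly enrolled and switched, match the reconciled text. If any such child has already been dosed under either reading, confirm the intervals actually given before the Week 16 and Week 48 summaries are produced.

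The cost is about one phrase in a table footnote and one system check. Sample size, visits and planned analyses do not change.
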